Patients who do not reach the required scores of  $\geq 24$  in MMSE and CDR total score 0 or 0.5 are not eligible for this study and must be registered as screen failure in IRT. If the result of the MMSE and CDR fulfill the requirements of the parallel trial 1289.7 and the patient and his study partner agree to alternatively participate in 1289.7 after giving a new consent then the results of the MMSE and CDR can be transferred into the database of 1289.7 without repeated performance of the MMSE and CDR and vice versa. This prevents the risk of unwanted learning effects which would be a consequence of repeating the MMSE and CDR in the same patient. This rule only applies if the screening visit for 1289.7 is no later than 7 days after the MMSE/CDR for 1289.5 was performed. The patient will then be registered as a new patient in the IRT of 1289.7. This does not apply to sites participating in only one of the 1289.5/1289.7 studies.

Permission to randomize more than 15 patients per site must be obtained in writing from the TCM at Boehringer Ingelheim. This will only be allowed after a careful review of the enrolment status.

Re-screening of not yet randomised patients can be allowed in exceptional cases but should be discussed on a case-by-case basis between the study site, Monitor staff and with the TCM.

A log of all patients included into the study (i.e. having given informed consent) will be maintained in the ISF at the investigational site irrespective of whether they have been treated with investigational drug or not.

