### 3.3.2 Inclusion criteria

Patients will be included in this study if they meet all of the following criteria:

1. Male and female patients with an age  $\geq 55$  years. Patients older than 85 years may be included based on an acceptable general health status, (e.g. concomitant diseases, physical capability to follow the required study procedures [visits etc.]) per investigators judgement.
2. Body weight  $\geq 50$  kgs.

Proprietary confidential information.

© 2017 Boehringer Ingelheim International GmbH or one or more of its affiliated companies. All rights reserved.

This document may not - in full or in part - be passed on, reproduced, published or otherwise used without prior written permission.

3. Patients with a confirmed diagnosis of prodromal AD on neuropsychological testing defined as:

- Mini-Mental State Examination (MMSE) score:  $\geq 24$   
and
- a global CDR-score of 0 or 0.5  
and
- Free and Cued Selective Recall Reminding Test (FCSRT) score:
  - free recall test:  $\leq 20$  (out of 48) and
  - total recall test:  $\leq 42$  (out of 48)

Patients who do not reach the required score in FCSRT will additionally perform the Wechsler Memory Visual Paired Associates test. If the Wechsler Memory Visual Paired Associates test shows a cognitive deficit worse than 1 standard deviation to the mean (compared to the reference values of age and educational norms for inclusion), then the patients can be considered to be eligible for the study. [\[R14-4676\]](#)

4. Confirmation of abnormal markers of AD pathology either via a), or alternatively b) mentioned below:\*

a) Presence in cerebrospinal fluid of (samples taken within past 4 months may be eligible, refer to [section 5.6.1](#) and [appendix 10.2](#) for full details):

- low A $\beta$ 1-42 concentrations ( $< 640$  pg/mL) and increased total tau concentrations ( $> 375$  pg/ml),

or / and

- low A $\beta$ 1-42 concentrations ( $< 640$  pg/mL) and increased phospho-tau concentrations ( $> 52$  pg/mL in cerebrospinal fluid),

or

b) Abnormal amyloid deposition in a cerebral PET scan. Scans performed in the past according to the recommendations in [section 5.3.2.1](#) are acceptable.

\* Note – CSF or PET could be the procedure of choice as per local regulations or IRBs/ IECs or site practices (as applicable).

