### 6.2.1 Screening and run-in period(s)

#### Visit 1 (screening)

- No trial procedures should be done unless the patient and study partner have consented to taking part in the trial.
- Once the patient has consented, the patient is considered to be enrolled in the trial and has started screening. The patient should be recorded on the enrolment log and be registered in the IRT as a screened patient.
- Informed consent for optional pharmacogenomics sampling, if applicable should be obtained.
- For diabetic patients with antidiabetic therapy: exclusion of hypoglycemia for the period of the neuropsychological assessment (documented plasma glucose concentration  $\geq 90$  mg/dl (5mmol/l) at the beginning and directly after the assessment). If glucose is too low patients need to eat a snack and then be retested to confirm that the blood sugar value is above 90 mg/dl before the tests are started
- The following screening procedures must however be performed in the order of the [Flow Chart](#): MMSE, FCSRT, (Wechsler Memory Visual Paired Associates test, if applicable), CDR, ADAS-cog11, MRI/CCT and PET/ CSF sampling (whichever applicable) to ensure that undesirable, invasive screening procedures are deferred until necessary.
- If the patient fails screening due to the results of the MMSE and/or the CDR then an alternative participation in study 1289.7 might be considered, where applicable.
- Administration of C-SSRS (baseline/screening scale)
- Collection of urine and blood for safety laboratory testing including testing for HIV, Syphilis and vitamin B12 and folate levels.
- Collection of blood samples for optional soluble biomarker evaluation from patients who consent.
- If patient does not meet inclusion/exclusion criteria at visit 1 then the patient must be recorded in IRT and CRFs as a screen failure.
- If the patient is eligible according to inclusion/exclusion criteria available at visit 1, the run-in visit (visit 2) should be scheduled. Patient should be reminded to come for visit 2 in the morning.
- Patients are allowed to have a light breakfast/ meal before coming to the study site.
- Patients should be reminded not to take occasionally used sleeping aids (see [section 4.2.2.1](#)) in the evening prior to visit 2.
- Patient should be reminded to inform the study site in case of adverse events.

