#### Primary analysis model

The restricted maximum likelihood (REML) based mixed effects model with repeated measurements (MMRM) will be used for the change from baseline in NTB total score after 12 weeks of treatment. The model will include fixed, categorical effects of treatment, visit and treatment by visit interaction, as well as the continuous fixed covariates of baseline and baseline-by-visit interaction. Patient will be considered as random effect. The unstructured covariance structure will be used to model the within patient errors. If this analysis fails to converge, compound symmetry covariance structure might be used. The Kenward-Roger approximation will be used to estimate denominator degrees of freedom. Analyses will be implemented using SAS PROC MIXED. The primary treatment comparisons will be the contrast between treatments after 12 weeks of treatment. Adjusted mean values as well as treatment contrasts will be presented together with the 95 % confidence intervals.

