#### 7.6 DETERMINATION OF SAMPLE SIZE

The primary efficacy hypothesis will be tested by comparing the dose group of BI 409306 with the peak response in the fitted regression model to the placebo group on the primary

Proprietary confidential information.

© 2017 Boehringer Ingelheim International GmbH or one or more of its affiliated companies. All rights reserved.

This document may not - in full or in part - be passed on, reproduced, published or otherwise used without prior written permission.

endpoint, the change from baseline in NTB total score after 12-week treatment. (See [section 7.2](#) for the details of hypothesis testing.)

As previously mentioned, the randomization allocation ratio of 1:1:1:1:2 of 10 mg, 25 mg, 50 mg, 25 mg BID of BI 409306, and placebo is used so that 33 % of patients will be randomized to placebo. Since these results in an unequal allocation of treatment to placebo, the sample size required for the active treatment and placebo for various effect size are displayed separately. The sample size calculations in [Table 7.6:1](#) displays the range of effect sizes considered for this trial under these assumptions using a 2-sided alpha of 0.05 with 80 % power. The two-sample t-test method with unequal n's in nQuery Advisor 6.01 was used for the calculation.

Table 7.6: 1 Sample size calculations

Standardized effect size	0.45	0.50	0.55	0.6	0.65
Power	80%	80%	80%	80%	80%
n for each active treatment arm	59	48	40	34	29
n for placebo arm	118	96	80	68	58
Total	354	288	240	204	174

Based on the calculations provided in [Table 7.6:1](#), a sample size of 48 per active treatment arm and 96 for placebo arm was selected as adequate for a phase II proof of concept trial. This sample size would allow us to detect an effect size of 0.5 with 80 % power or an effect size of 0.6 with 92 % power, 2-sided alpha at 0.05.

*Assuming a 10% dropout rate, this sample size would allow us to detect an effect size of 0.53 with 80% power and assuming a 20% dropout rate, this sample size would allow us to detect an effect size of 0.56 with 80% power, 2-sided alpha at 0.05.*

Proprietary confidential information.

© 2017 Boehringer Ingelheim International GmbH or one or more of its affiliated companies. All rights reserved.  
This document may not - in full or in part - be passed on, reproduced, published or otherwise used without prior written permission.

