9 ADDITIONAL SECTIONS

9.1 CALCULATION OF NTB TOTAL SCORE

Below is a description for the NTB along with detail on deriving the scores for the total scores and several subscales. The derivations are based on [6] and the supplementary information from [7].

Table 9.1: 1 NTB description and scoring

The NTB is a cognitive assessment made up of the following 9 component tests:

1. Wechsler Memory Scale Visual Paired Associates—Immediate (WMVis-I), range 0 to 18;
2. Wechsler Memory Scale Verbal Paired Associates—Immediate (WMVer-I), range 0 to 24;
3. Rey Auditory Verbal Learning Test—Immediate (RAVL-I), range 0 to 105;
4. Wechsler Memory Scale—Digit Span (WMDS), range 0 to 24;
5. Controlled Word Association Test (COWAT);
6. Category Fluency Test (CFT);
7. Wechsler Memory Scale Visual Paired Associates—Delayed (WMVis-D), range 0 to 6;
8. Wechsler Memory Scale Verbal Paired Associates—Delayed (WMVer-D), range 0 to 8;
9. Rey Auditory Verbal Learning Test—Delayed (RAVL-D), range 0 to 30.

The first 3 tests assess immediate memory (WMVis-I, WMVer-I, RAVL-I), the second 3 assess executive function (WMDS, COWAT, CFT), and the last 3 assess delayed memory (WMVis-D, WMVer-D, RAVL-D). Higher scores indicate better cognition on all tests.

First, a total score for each component test except the RAVL-D is calculated by summing all the scores. For the RAVL-D, the total score is calculated as:

total part 7 + total part 8 correct + (15 - total part 8 incorrect).

Then, a z-score for each component test is calculated as follows. For each subject j , at assessment time point t (with $t = 0$ denoting baseline), let y_{ijt} denote subject j 's score at time t for the i th component test ($i = 1, \dots, 9$). Then the corresponding z-score, denoted z_{ijt} , is defined as:

$$z_{ijt} = (y_{ijt} - \bar{y}_{ij\theta}) / s_{ij\theta}$$

Proprietary confidential information © 2017 Boehringer Ingelheim International GmbH or one or more of its affiliated companies

Where y_{i0} and s_{i0} denote the average and the standard deviation of the baseline scores on the i th component test across all study subjects in the FAS.

Finally, the NTB total score z_{jt} for the j th subject at time t is calculated by averaging the 9 component test z-scores:

$$z_{ijt} = (z_{1jt} + \dots + z_{9jt})/9$$

The NTB total z-score will be calculated only if scores for at least 6 of the 9 component tests are not missing [6].

In addition, the following subscales are defined:

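### The primary NTB model adjusts only for baseline NTB, although every patient also has a pre-treatment FCSRT memory score that could add a little precision at almost no cost

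*Protocol*

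**What the plan says.** **Screening.** Protocol 6.2.1 (Visit 1) fixes the order of the eligibility tests as "MMSE, FCSRT, (Wechsler Memory Visual Paired Associates test, if applicable), CDR", followed by ADAS-cog11, imaging and the biomarker procedure. The FCSRT is therefore taken by everyone. Under Protocol 3.3.2, criterion 3, "Patients who do not reach the required score in FCSRT will additionally perform the Wechsler Memory Visual Paired Associates test", and they may be eligible if that test shows a deficit of more than 1 SD against norms.

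**Endpoint.** The primary endpoint is change in NTB total z-score from Visit 3 to Week 12. The total averages nine component z-scores. SAP 9.1 lists "Wechsler Memory Scale Visual Paired Associates" twice among the nine: the immediate part as component 1 and the delayed part as component 7.

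**Model.** Protocol 7.3.1 specifies an MMRM with treatment, visit and their interaction, "as well as the continuous fixed covariates of baseline and baseline-by-visit interaction". SAP 7.4.1 refers back to that section. The MMRM code in SAP Table 9.3.1 contains neither an FCSRT term nor a term for qualification route. The dose-response code in the same table has only dose and dose squared on the right-hand side. Randomisation is unstratified (Protocol 7.5).

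**Sample size.** Protocol 7.6 chooses "a sample size of 48 per active treatment arm and 96 for placebo arm" and says this can "detect an effect size of 0.5 with 80 % power or an effect size of 0.6 with 92 % power".

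**The concern.** The endpoint is largely a memory measure: six of its nine components are memory tests. The trial also records a separate memory test on every patient before treatment and then leaves it out of the analysis. If FCSRT predicts Week 12 NTB change beyond what baseline NTB already explains, leaving it out keeps avoidable residual variance in each dose-placebo contrast. The design has little room: 80% power at effect size 0.5 is the figure before dropout.

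Step 2 is barer still. Protocol 7.2 bases Steps 1 and 3 on adjusted means from the primary model, but the Step 2 regression, as coded, adjusts for nothing, not even baseline NTB. Step 2 determines which dose is tested in Step 3.

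A smaller matter sits beside this. Patients who enter through the back-up test have met Visual Paired Associates at Visit 1, so for them Visit 3 is a repeat of that test within the trial; for the others it is normally the first. Any practice gain may then fall before baseline in one group and after it in the other, which adds some variance to the change score.

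**Working it through.** **1. Reproduce the plan's figure.** Inputs from Protocol 7.6: "using a 2-sided alpha of 0.05 with 80 % power", 48 against 96 patients, effect size d = 0.5, two-sample t-test with unequal n.

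- Noncentrality = d / √(1/48 + 1/96) = 0.5 / √0.03125 = 2.828.
- Degrees of freedom 142; critical t = 1.977.
- Noncentral-t power = **80.2%**; at d = 0.6, 92.1%. Both agree with the protocol. All five columns of Table 7.6:1 also reproduce (59, 48, 40, 34 and 29 per active arm).

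**2. Add FCSRT.** Let r be the partial correlation of FCSRT with Week 12 NTB change, given baseline NTB. Residual SD is multiplied by √(1 − r²), so the effective d is 0.5 / √(1 − r²). This treats 0.5 as standardised by the residual SD of the current model. The documents give no value for r; the range is an assumption.

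| r (assumed) | Residual variance removed (r²) | Effective d | Power, 48 vs 96 | Equivalent extra patients, 288 × [1/(1 − r²) − 1] |
|---|---|---|---|---|
| 0 | 0 | 0.500 | 80.2% | 0 |
| 0.10 | 1.0% | 0.503 | 80.6% | 2.9 |
| 0.20 | 4.0% | 0.510 | 81.8% | 12.0 |
| 0.25 | 6.3% | 0.516 | 82.7% | 19.2 |

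If the covariate proves useless, dropping from 142 to 141 degrees of freedom leaves power at 80.2%.

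**3. Size the Visual Paired Associates overlap.** Assumptions, none given in the documents: practice gain differs between routes by g = 0.2 to 0.4 SD on each of the two components, and a share p = 10% to 50% of patients enters by the back-up route.

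- Difference in NTB total change between routes = 2g/9 = 0.044 to 0.089 z.
- SD of the chance difference in share between one active arm and placebo = √[p(1 − p)(1/48 + 1/96)] = 0.053 (p = 0.1) to 0.088 (p = 0.5).
- Typical shift in the contrast = 0.053 × 0.044 to 0.088 × 0.089 = **0.002 to 0.008 z**.

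For the precision effect, take a wider range: g = 0.2 to 0.5, the same p, and an assumed SD of change of 0.3 to 0.5 z. Share of variance due to route = p(1 − p)(2g/9)² / SD². This runs from 0.09 × 0.044² / 0.25 = 0.1% to 0.25 × 0.111² / 0.09 = 3.4%. Removing all of it gives power of 80.2% to 81.6%.

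**4. Step 2.** The documents do not give the correlation between baseline NTB and NTB change, so the gain from adding baseline there cannot be sized. The direction is clear: the covariate judged worth having in the MMRM is missing from the regression that selects the dose.

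**The case against.** The strongest reply is that omitting an optional covariate is a design choice. The trial calls itself exploratory and treats its p-values as descriptive. Baseline NTB already averages six memory tests, and patients on the main route are restricted to FCSRT free recall of 20 or less, so FCSRT may add little; at r = 0.10 the gain is 0.4 percentage points. All of this stands, and it is why the point is a suggestion for improvement.

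A reader might go further and infer that the back-up test contaminates the primary endpoint or biases the comparison. The documents do not support that:

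- The Visit 1 exposure precedes randomisation, so it is balanced across arms in expectation, and baseline NTB absorbs part of it.
- They do not say whether the delayed part is given at screening (if not, 2/9 becomes 1/9) or whether the same form is used. Administration detail is in manuals in the site file.
- Selection on a low score at Visit 1 comes before the Visit 3 baseline, so regression from that score to Visit 3 is not part of the change score.

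Nor does Protocol 3.3 contradict the schedule. Its remark, "This prevents the risk of unwanted learning effects which would be a consequence of repeating the MMSE and CDR in the same patient", concerns patients moving between trials 1289.5 and 1289.7. The protocol itself gives ADAS-cog11 at both Visit 1 and Visit 3.

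Two limits also stand. A route indicator overlaps with FCSRT, because route is decided by the FCSRT cut-offs; it is not fully redundant with free recall, since missing the total-recall cut-off also sends a patient to the back-up test. And parts of the SAP, including a subsection after 7.4.1, are redacted and may hold sensitivity or subgroup analyses. The primary model itself is readable and lacks both terms.

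**Conclusion.** The point holds as a minor gain in precision. The primary MMRM adjusts only for baseline NTB and its visit interaction, and the Step 2 code adjusts for nothing, although a pre-treatment FCSRT score exists for every patient. With r between 0.10 and 0.25, power at effect size 0.5 moves from 80.2% to 80.6–82.7%, comparable to 3 to 19 more patients. That range depends wholly on r, which the documents do not give.

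The Visual Paired Associates overlap is real but small: a typical chance shift of 0.002–0.008 z, and at most about 1.4 points of power under favourable assumptions. It gives no ground for doubting the validity of the randomised contrast. The joint gain from both terms was not computed and, because they overlap, should not be obtained by adding the two.

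**What to change.** Before unblinding, amend SAP 7.4.1 and Table 9.3.1 as follows:

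1. Add Visit 1 FCSRT free recall as a continuous covariate in the NTB MMRM.
2. Add baseline NTB and FCSRT free recall to the Step 2 dose-response regression.
3. Optionally, add a yes/no indicator for having taken Visual Paired Associates at Visit 1.

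Keep change from Visit 3 as the endpoint. State how a missing FCSRT value is handled, so that no patient drops out of the model because of it; few should be missing, since the test is part of eligibility. While Table 9.3.1 is open, note that its MMRM code lists baseline twice where Protocol 7.3.1 specifies a baseline-by-visit term, and align the two.

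The cost is SAP wording and about one degree of freedom in the MMRM for FCSRT (one more for the optional indicator, and another if it is crossed with visit). No new data, visits or patient burden are needed.

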#### Visit 2 (Run-in period)

- It is recommended to perform study procedures in the order as listed in the [Flow Chart](#).

Proprietary confidential information.

© 2017 Boehringer Ingelheim International GmbH or one or more of its affiliated companies. All rights reserved.

This document may not - in full or in part - be passed on, reproduced, published or otherwise used without prior written permission.

- Results pending for assessments done at visit 1 for inclusion/ exclusion criteria should be evaluated and if the patient is deemed ineligible, the patient must be recorded in IRT and CRFs as a screen failure.
- If patient does not meet inclusion/exclusion criteria available on visit 2 the patient must be recorded in IRT and CRFs as a screen failure.
- Informed consent for optional pharmacogenomics sampling, if applicable should be obtained
- Administration of C-SSRS (since last visit scale).
- The intake of trial medication and handling of medication blisters should be discussed with the patient and the study partner. The first dose of the trial medication should be taken by the patient under the supervision of the study. Patients should be advised to take the trial medication as per the drug label till the next scheduled visit. The importance of compliance to the study drug intake should be emphasized to the study partner as well.
- Patients should be reminded to get all used and un-used medication including the medication packaging back at visit 3.
- Patients should be reminded not to take occasionally used sleeping aids (see [section 4.2.2.1](#)) in the evening prior to visit 3.
- Patients should be reminded to NOT take any study medication on the morning of visit 3.
- Patients are allowed to have a light breakfast/ meal before coming to the study site.
- Patient should be reminded to inform the study site in case of adverse events.

### 6.2.2 Treatment period(s)

#### Visit 3 (Randomization visit)

Visit 3 is the baseline/randomisation visit and marks the beginning of the treatment period. The neuropsychological assessments may be done on the day before the randomisation visit (last day of the screening period) if agreed between site staff and patient. In any case it needs to be ensured that the recommendations for the conduct of the neuropsychological assessments (refer to [section 6.2](#) for details) are followed.

- It is recommended to perform study procedures in the order as listed in the [Flow Chart](#).
- Study medication provided at visit 2 and returned should be collected and compliance check performed.
- Beginning with Visit 3 until end of treatment (EOT/ ED respectively) the neuropsychological assessments should always be performed approximately at the same time (in the morning) in the order as stated in the [Flow Chart](#)
- Eligible patients should be randomised using IRT. If patient does not meet inclusion/exclusion criteria at visit 3 the patient must be recorded in IRT and CRFs as a screen failure.
- Informed consent for optional pharmacogenomics sampling, if applicable should be obtained
- For diabetic patients with antidiabetic therapy: exclusion of hypoglycemia for the period of the neuropsychological assessment (documented plasma glucose concentration  $\geq 90$  mg/dl (5mmol/l) at the beginning and directly after the assessment). If glucose is too low

Proprietary confidential information.

© 2017 Boehringer Ingelheim International GmbH or one or more of its affiliated companies. All rights reserved.  
This document may not - in full or in part - be passed on, reproduced, published or otherwise used without prior written permission.

patients need to eat a snack and then be retested to confirm that the blood sugar value is above 90 mg/dl before the tests are started

- Administer the neuropsychological assessments in the following order :
  - CDR-SB
  - NTB
  - ADCS-MCI-ADL
  - ADAS-cog11
- Administration of C-SSRS (since last visit scale).
- Pre-dose vital signs (orthostatic measurements of systolic/diastolic blood pressure and pulse rate). Please see [section 5.2.5.2](#).
- [REDACTED]
- [REDACTED]
- Collection of urine and blood for safety laboratory testing.
- [REDACTED]
- [REDACTED]
- New medication kits should be dispensed and the intake of trial medication and handling of medication blisters should be discussed with the patient and the study partner.
- The first dose of the study medication from the new kit should be taken under the supervision of the study staff.
- [REDACTED]
- Post Dose Vital Signs\_(orthostatic measurements of systolic/diastolic blood pressure and pulse rate) at 70-110 minutes should be performed. Please see [section 5.2.5.2](#).
- Patients should be advised to take the trial medication as per the drug label till the next scheduled visit. The importance of compliance to the study drug intake should be emphasized to the study partner as well. Patients should be reminded to return all used and un-used medication including the medication packaging back to the clinic at visit 5.
- Patients should be reminded not to take occasionally used sleeping aids (see [section 4.2.2.1](#)) in the evening prior to visit 5
- Patient should be reminded to NOT take any study medication on the morning of visits 4 and 5.
- Patients are allowed to have a light breakfast/ meal before coming to the study site.
- Patient should be reminded to inform the study site in case of adverse events.

